9.5 Interim Monitoring

Study data will be reviewed by DSMC twice a year during the first 2 years of study activation, and once a year thereafter if no concerns are identified.

The study will be conducted in two stages: a randomized *screening* stage, and a larger *confirmatory* stage. The screening stage will compare the proportion of Stage 1-4 GI aGvHD between the 2 arms. The proportion of 120 centrally reviewed, eligible and evaluable randomized patients having Stage 1-4 GI aGvHD incidence from Day 0 through Day 120 will be compared between the two arms via two-sample test of proportions at 1-sided $\alpha=0.3$. If the screening stage suggests efficacy ($p<0.3$), the study will proceed to the confirmatory stage ($N=454$). If efficacy is not established at the screening stage, the data will be referred to the COG Data Safety and Monitoring Committee (DSMC) for consideration of early termination.

Amendment 1: Haploidentical transplantation in children has increased over the past few years. Although single institution studies have demonstrated a remarkably lower acute and chronic Graft vs Host Disease incidence and severity, these results have not been duplicated in larger multicenter trials. In these multicenter trials, the Grade II-IV Acute GvHD rate does not appear to be significantly different from that of other alternative donor trials. While we do agree that the rate of chronic GVH appears much less, our current study ends at Day + 120 and thus chronic GVH is not measured in this trial.

Therefore, it is presumed to have no impact on the power for the primary aim by having haploidentical patients enrolled in this study. The estimated primary outcome rate aGvHD and proportion of haploidentical patients will be monitored bi-annually. At each monitoring time, by assuming the observed aGvHD rate, proportion of haploidentical patients within the control arm, and using the same power simulation (that we've used to provide power analysis for the protocol), if the estimated power at the end of the study is less than 80%, we will adjust the sample size through an Amendment. All observed rates will be available only for members of DSMC to review.

9.6 Gender and Minority Accrual Estimates

DOMESTIC PLANNED ENROLLMENT REPORT

Racial Categories	Ethnic Categories				Total
	Hispanic or Latino		Not Hispanic or Latino		
	Female	Male	Female	Male	
American Indian/ Alaska Native	0	0	0	0	0
Asian	0	0	16	16	32
Native Hawaiian or Other Pacific Islander	0	0	0	0	0
Black or African American	0	16	63	111	190
White	95	16	47	95	253
More Than One Race	0	0	0	0	0
Total	95	32	126	222	475

INTERNATIONAL (INCLUDING CANADA) PLANNED ENROLLMENT REPORT

Racial Categories	Ethnic Categories				Total
	Hispanic or Latino		Not Hispanic or Latino		
	Female	Male	Female	Male	
American Indian/ Alaska Native	0	0	0	0	0
Asian	0	0	1	1	2
Native Hawaiian or Other Pacific Islander	0	0	0	0	0
Black or African American	0	1	3	6	10
White	5	1	2	5	13
More Than One Race	0	0	0	0	0
Total	5	2	6	12	25

This distribution was derived from the pilot study data, adjusted for Children's Oncology Group projections.

10.0 EVALUATION CRITERIA

10.1 Common Terminology Criteria for Adverse Events (CTCAE)

This study will utilize version 5.0 of the CTCAE of the National Cancer Institute (NCI) for toxicity and performance reporting. A copy of the CTCAE version 5.0 can be downloaded from the CTEP website

(http://ctep.cancer.gov/protocolDevelopment/electronic_applications/ctc.htm).

Additionally, toxicities are to be reported on the appropriate case report forms.

Please note: 'CTCAE v5.0' is understood to represent the most current version of CTCAE v5.0 as referenced on the CTEP website (i.e., v5.02 and all subsequent iterations prior to version 6.0).

10.2 Acute GVHD

See [Appendix III](#) protocol specific staging and grading criteria for acute GVHD.

10.3 Graft Failure

Primary Graft Failure

Failure to achieve an ANC $\geq 500/\mu\text{L}$ after 42 days, determined by three consecutive measurements on different days; or $< 5\%$ donor cells in blood or bone marrow by Day +42 (as demonstrated by a chimerism assay), without evidence of JMML.

Secondary Graft Failure

Initial engraftment followed by severe neutropenia (ANC $\leq 500/\mu\text{L}$) that is not caused by recurrent leukemia, or $< 5\%$ donor cells in the blood or bone marrow (as demonstrated by a chimerism assay) without subsequent improvement occurring either spontaneously or after growth factor treatment. Improvement is defined as ANC $> 500/\mu\text{L}$ consistently. Severe neutropenia with bone marrow cellularity $\geq 25\%$ is not secondary graft failure.

Marrow, UCB or peripheral blood stem cell reinfusion carried out any time after Day 0 because of inadequate hematopoietic function will be taken as a definitive indication of graft failure regardless of AMC values and marrow cellularity. Donor lymphocyte infusion is not considered a stem cell reinfusion.

11.0 ADVERSE EVENT REPORTING REQUIREMENTS

11.1 Purpose

Adverse event data collection and reporting, which are required as part of every clinical trial, are done to ensure the safety of patients enrolled in the studies as well as those who will enroll in future studies using similar agents. Certain adverse events must be reported in an expedited manner to allow for timelier monitoring of patient safety and care. The following sections provide information about expedited reporting.

11.2 Expedited Reporting Requirements – Serious Adverse Events (SAEs)

To ensure compliance with these regulations/this guidance, NCI requires that AEs be submitted according to the timeframes in the AE reporting tables assigned to the protocol, using the CTEP Adverse Event Reporting System (CTEP-AERS).

Any AE that is serious qualifies for expedited reporting. An AE is defined as any untoward medical occurrence associated with the use of a drug in humans, whether or not considered drug related. A Serious Adverse Event (SAE) is any adverse drug event (experience) occurring at any dose that results in ANY of the following outcomes:

- 1) Death.
- 2) A life-threatening adverse drug experience.
- 3) An adverse event resulting in inpatient hospitalization or prolongation of existing hospitalization (for ≥ 24 hours). This does not include hospitalizations that are part of routine medical practice.
- 4) A persistent or significant incapacity or substantial disruption of the ability to conduct normal life functions.
- 5) A congenital anomaly/birth defect.
- 6) Important Medical Events (IME) that may not result in death, be life threatening, or require hospitalization may be considered a serious adverse drug experience when, based upon medical judgment, they may jeopardize the patient or subject and may

require medical or surgical intervention to prevent one of the outcomes listed in this definition.

11.3 Specific Examples for Expedited Reporting

11.3.1 SAEs Occurring More than 30 Days After Last Dose of Study Drug

Any Serious Adverse Event that occurs more than 30 days after the last administration of the investigational agent/intervention **and** has an attribution of a possible, probable, or definite relationship to the study therapy must be reported according to the CTEP-AERS reporting tables in this protocol.

11.3.2 Persistent or Significant Disabilities/Incapacities

Any AE that results in persistent or significant incapacity or substantial disruption of the ability to conduct normal life functions (formerly referred to as disabilities), congenital anomalies or birth defects, must be reported via CTEP-AERS if it occurs at any time following treatment with an agent under a NCI, COG, or industry sponsor IND/IDE since these are considered to be serious AEs.

11.3.3 Death

Reportable Categories of Death

- Death attributable to a CTCAE term.
- Death Neonatal: Newborn death occurring during the first 28 days after birth.
- Sudden Death NOS: A sudden (defined as instant or within one hour of the onset of symptoms) or an unobserved cessation of life that cannot be attributed to a CTCAE term associated with Grade 5.
- Death NOS: A cessation of life that cannot be attributed to a CTCAE term associated with Grade 5.
- Death due to progressive disease should be reported as *Grade 5 "Disease progression"* in the system organ class (SOC) "*General disorders and administration site conditions.*" Evidence that the death was a manifestation of underlying disease (e.g., radiological changes suggesting tumor growth or progression: clinical deterioration associated with a disease process) should be submitted.

Any death occurring **within 30 days** of the last dose, regardless of attribution to the investigational agent/intervention requires expedited reporting within 24 hours.

Any death occurring **greater than 30 days** after the last dose of the investigational agent/intervention requires expedited reporting within 24 hours **only if** it is possibly, probably, or definitely related to the investigational agent/intervention.

11.3.4 Secondary Malignancy

A **secondary malignancy** is a cancer caused by treatment for a previous malignancy (e.g., treatment with investigational agent/intervention, radiation or chemotherapy). A metastasis of the initial neoplasm is not considered a secondary malignancy.

All secondary malignancies that occur following treatment need to be reported via CTEP-AERS. Three options are available to describe the event:

- Leukemia secondary to oncology chemotherapy
- Myelodysplastic syndrome
- Treatment related secondary malignancy

Any malignancy possibly related to cancer treatment (including AML/MDS) must also be reported via the routine reporting mechanisms outlined in this protocol.

11.3.5 Second Malignancy

A **second malignancy** is one unrelated to the treatment of a prior malignancy (and is NOT a metastasis from the initial malignancy). Second malignancies require ONLY routine reporting via CDUS unless otherwise specified.

11.3.6 Pregnancy, Pregnancy Loss, and Death Neonatal

NOTE: When submitting CTEP-AERS reports for “Pregnancy”, “Pregnancy loss”, or “Death Neonatal”, the Pregnancy Information Form, available at http://ctep.cancer.gov/protocolDevelopment/electronic_applications/docs/PregnancyReportForm.pdf, needs to be completed and faxed along with any additional medical information to [contact]. The potential risk of exposure of the fetus to the investigational agent(s) or chemotherapy agent(s) should be documented in the “Description of Event” section of the CTEP-AERS report.

11.3.6.1 **Pregnancy**

Patients who become pregnant on study risk intrauterine exposure of the fetus to agents that may be teratogenic. For this reason, pregnancy needs to be reported in an expedited manner via CTEP-AERS as **Grade 3 “Pregnancy, puerperium and perinatal conditions - Other (pregnancy)”** under the ***Pregnancy, puerperium and perinatal conditions*** SOC.

Pregnancy needs to be followed **until the outcome is known**. If the baby is born with a birth defect or anomaly, then a second CTEP-AERS report is required.

11.3.6.2 **Pregnancy Loss (Fetal Death)**

Pregnancy loss is defined in CTCAE as “*Death in utero.*” Any Pregnancy loss should be reported expeditiously as **Grade 4 “Pregnancy loss”** under the ***Pregnancy, puerperium and perinatal conditions*** SOC. Do NOT report a pregnancy loss as a Grade 5 event since CTEP-AERS recognizes any Grade 5 event as a patient death.

11.3.6.3 **Death Neonatal**

Neonatal death, defined in CTCAE as “*Newborn death occurring during the first 28 days after birth*” should be reported expeditiously as **Grade 4 “Death neonatal”** under the ***General disorders and administration*** SOC **when the death is the result of a patient pregnancy or pregnancy in partners of men on study**. Do NOT report a neonatal death resulting from a patient pregnancy or pregnancy in partners of men on study as a Grade 5 event since CTEP-AERS recognizes any Grade 5 event as a patient death.

11.4 Reporting Requirements for Specialized AEs

11.4.1 Baseline AEs

Although a pertinent positive finding identified on baseline assessment is not an AE, when possible it is to be documented as “Course Zero” using CTC/AE terminology and grade. An expedited AE report is not required if a patient is entered on a protocol with a pre-existing condition (e.g., elevated laboratory value, diarrhea). The baseline AE must be re-assessed throughout the study and reported if it fulfills expedited AE reporting guidelines.

- a. If the pre-existing condition worsens in severity, the investigator must reassess the event to determine if an expedited report is required.
- b. If the AE resolves and then recurs, the investigator must re-assess the event to determine if an expedited report is required.
- c. No modification in grading is to be made to account for abnormalities existing at baseline.

11.4.2 Persistent AEs

A persistent AE is one that extends continuously, without resolution between treatment cycles/courses.

ROUTINE reporting: The AE must be reported only once unless the grade becomes more severe in a subsequent course. If the grade becomes more severe the AE must be reported again with the new grade.

EXPEDITED reporting: The AE must be reported only once unless the grade becomes more severe in the same or a subsequent course.

11.4.3 Recurrent AEs

A recurrent AE is one that occurs and resolves during a cycle/course of therapy and then reoccurs in a later cycle/course.

ROUTINE reporting: An AE that resolves and then recurs during a subsequent cycle/course must be reported by the routine procedures.

EXPEDITED reporting: An AE that resolves and then recurs during a subsequent cycle/course does not require CTEP-AERS reporting unless:

- 1) The grade increases OR
- 2) Hospitalization is associated with the recurring AE.

11.5 Exceptions to Expedited Reporting

An expedited report may not be required for a specific protocol where an AE is listed as expected. The exception or acceptable reporting procedures will be specified in the protocol. The protocol specific guidelines supersede the NCI Adverse Event Reporting Guidelines. These special situations are listed under the CTEP-AERS reporting Table A for this protocol.

11.6 Reporting Requirements - Investigator Responsibility

Clinical investigators in the treating institutions and ultimately the Study Chair have the primary responsibility for AE identification, documentation, grading, and assignment of attribution to the investigational agent/intervention. It is the responsibility of the treating physician to supply the medical documentation needed to support the expedited AE reports in a timely manner.

Note: All expedited AEs (reported via CTEP-AERS) must also be reported via routine reporting. Routine reporting is accomplished via the Adverse Event (AE) Case Report Form (CRF) within the study database.

11.7 General Instructions for Expedited Reporting via CTEP-AERS

The reporting methods described below are specific for clinical trials evaluating agents for which the IND is held by COG, an investigator, or a pharmaceutical company. It is important to note that these procedures differ slightly from those used for reporting AEs for clinical trials for which CTEP holds the IND.

The descriptions and grading scales found in the revised NCI Common Terminology Criteria for Adverse Events (CTCAE) version 5.0 will be utilized for AE reporting. All appropriate treatment areas should have access to a copy of the CTCAE version 5.0. A copy of the CTCAE version 5.0 can be downloaded from the CTEP website at: http://ctep.cancer.gov/protocolDevelopment/electronic_applications/ctc.htm.

An expedited AE report must be submitted electronically via CTEP-AERS at: <https://eapps-ctep.nci.nih.gov/ctepaers>

- Expedited AE reporting timelines are defined as:
 - **24-Hour; 5 Calendar Days** - The AE must initially be reported via CTEP-AERS within 24 hours of learning of the event, followed by a complete expedited report within 5 calendar days of the initial 24-hour report.
 - **7 Calendar Days** - A complete expedited report on the AE must be submitted within 7 calendar days of the investigator learning of the event.
- Any event that results in a persistent or significant incapacity/substantial disruption of the ability to conduct normal life functions, or a congenital anomaly/birth defect, or is an IME, which based upon the medical judgment of the investigator may jeopardize the patient and require intervention to prevent a serious AE, must be reported via CTEP-AERS **if the event occurs following investigational agent administration.**
- Any death occurring within 30 days of the last dose, regardless of attribution to an agent/intervention requires expedited reporting **within 24 hours** via e-mail to the COG CTEP-AERS Coordinator and Study Chair.
- Any death occurring greater than 30 days of the last dose with an attribution of possible, probable, or definite to an agent/intervention requires expedited reporting **within 24 hours** via e-mail to the COG CTEP-AERS Coordinator and Study Chair.

CTEP-AERS Medical Reporting includes the following requirements as part of the report: 1) whether the patient has received at least one dose of an investigational agent on this study; 2) the characteristics of the adverse event including the *grade* (severity), the *relationship to the study therapy* (attribution), and the *prior experience* (expectedness) of the adverse event; 3) the Phase (1, 2, or 3) of the trial; and 4) whether or not hospitalization or prolongation of hospitalization was associated with the event.

Fax or email supporting documentation **for AEs related to investigational agents** to COG: [contact]; email: [contact]; Attention: COG AERS Coordinator.

- **ALWAYS include the ticket number on all faxed documents.**
- **Use the NCI protocol number and the protocol-specific patient ID provided during trial registration on all reports.**

11.8 Reporting Table for Late Phase 2 and Phase 3 Studies – Table A

Expedited Reporting Requirements for Adverse Events that Occur on Studies under an IND/IDE within 30 Days of the Last Administration of the Investigational Agent/Intervention ¹

FDA REPORTING REQUIREMENTS FOR SERIOUS ADVERSE EVENTS (21 CFR Part 312)				
NOTE: Investigators MUST immediately report to the sponsor (COG) ANY Serious Adverse Events, whether or not they are considered related to the investigational agent(s)/intervention (21 CFR 312.64)				
An adverse event is considered serious if it results in ANY of the following outcomes:				
1) Death.				
2) A life-threatening adverse event.				
3) Any AE that results in inpatient hospitalization or prolongation of existing hospitalization for ≥ 24 hours. This does not include hospitalizations that are part of routine medical practice.				
4) A persistent or significant incapacity or substantial disruption of the ability to conduct normal life functions.				
5) A congenital anomaly/birth defect.				
6) Important Medical Events (IME) that may not result in death, be life threatening, or require hospitalization may be considered serious when, based upon medical judgment, they may jeopardize the patient or subject and may require medical or surgical intervention to prevent one of the outcomes listed in this definition. (FDA, 21 CFR 312.32; ICH E2A and ICH E6.)				
ALL SERIOUS adverse events that meet the above criteria MUST be immediately reported to the NCI via CTEP-AERS within the timeframes detailed in the table below.				
Hospitalization	Grade 1 Timeframes	Grade 2 Timeframes	Grade 3 Timeframes	Grade 4 & 5 Timeframes
Resulting in Hospitalization ≥ 24 hrs	7 Calendar Days			24-Hour Notification 5 Calendar Days
Not resulting in Hospitalization ≥ 24 hrs	Not Required		7 Calendar Days	
NOTE: Additional Special Situations as Exceptions to Expedited Reporting are listed below.				
Expedited AE reporting timelines are defined as:				
“24-Hour; 5 Calendar Days” - The AE must initially be reported via CTEP-AERS within 24 hours of learning of the AE, followed by a complete expedited report within 5 calendar days of the initial 24-hour notification.				
“7 Calendar Days” - A complete expedited report on the AE must be submitted within 7 calendar days of learning of the AE.				
¹ SAEs that occur more than 30 days after the last administration of investigational agent/intervention and have an attribution of possible, probable, or definite require reporting as follows:				
Expedited 24-hour notification followed by complete report within 5 calendar days for:				

 • All Grade 4, and Grade 5 AEs 				
Expedited 7 calendar day reports for:				

 • Grade 2 adverse events resulting in hospitalization or prolongation of hospitalization • Grade 3 adverse events 				

11.9 Protocol Specific Additional Instructions and Reporting Exceptions

- *LBP*-bacteremia will be considered an **unexpected severe adverse event**. Patients with a blood culture positive for *LBP* will cease to receive the probiotic immediately and the patient will be removed from protocol therapy. However, data collection will continue on all patients through Day 120, the final data point of the study. A report of *LBP*-bacteremia will initiate a sequence of monitoring events. Centers must report *LBP*-bacteremia within 24 hours of the diagnosis through the CTEP-AERS system.
- Only Grade 3 or 4 Unexpected Serious Adverse Events that are attributable (possibly, probably or definitely related) to *LBP* or the placebo should be reported.
- Any death, regardless of attribution should be reported.

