11.10 Routine Reporting of Adverse Events

Note: The guidelines below are for routine reporting of study specific adverse events on the COG case report forms and do not affect the requirements for CTEP-AERS reporting.

Routine reporting is accomplished via the Adverse Event (AE) Case Report Form (CRF) within the study database. For this study, routine reporting will include all CTEP-AERS reportable events and Grade 3 and higher Adverse Events that are possibly, probably or definitely attributable to the study product (*LBP* or placebo).

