12.2 Data Safety and Monitoring Committee

To protect the interests of patients and the scientific integrity for all clinical trial research by the Children’s Oncology Group, the COG Data and Safety Monitoring Committee (DSMC) reviews reports of interim analyses of study toxicity and outcomes prepared by the study statistician, in conjunction with the study chair’s report. The DSMC may recommend the study be modified or terminated based on these analyses.

Toxicity monitoring is also the responsibility of the study committee and any unexpected frequency of serious events on the trial are to be brought to the attention of the DSMC. The study statistician is responsible for the monitoring of the interim results and is expected to

request DSMC review of any protocol issues s/he feels require special review. Any COG member may bring specific study concerns to the attention of the DSMC.

The DSMC approves major study modifications proposed by the study committee prior to implementation (e.g., termination, dropping an arm based on toxicity results or other trials reported, increasing target sample size, etc.). The DSMC determines whether and to whom outcome results may be released

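### Section 11.9 narrows serious adverse event reporting below what Section 11.8 requires, and under 11.10 unattributed non-fatal events need not reach the adverse event form

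*Combined protocol and SAP*

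**What the plan says.** - Section 11.2 sets the general rule without an attribution condition: "Any AE that is serious qualifies for expedited reporting".
- The note at the head of Table A in Section 11.8 says: "Investigators MUST immediately report to the sponsor (COG) ANY Serious Adverse Events, whether or not they are considered related to the investigational agent(s)/intervention". It also sends serious events to the NCI within the table's timeframes. Table A covers events up to 30 days after the last dose. After that, its footnote and Section 11.3.1 ask only for attributed events.
- Section 11.9 says that "Only Grade 3 or 4 Unexpected Serious Adverse Events that are attributable (possibly, probably or definitely related) to" LBP or placebo should be reported. It separately requires LBP-bacteremia within 24 hours and adds: "Any death, regardless of attribution should be reported".
- Section 11.5 says: "The protocol specific guidelines supersede the NCI Adverse Event Reporting Guidelines". It places the exceptions under Table A and ties them to events listed as expected.
- Section 11.10 defines the routine form: "routine reporting will include all CTEP-AERS reportable events and Grade 3 and higher Adverse Events that are possibly, probably or definitely attributable" to study product.
- Section 11.3.3 asks for expedited notice of a death more than 30 days after the last dose only if "it is possibly, probably, or definitely related to the investigational agent/intervention". Section 11.7 says the same.
- Section 12.2 says: "any unexpected frequency of serious events on the trial are to be brought to the attention of the DSMC".

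**The concern.** A site cannot follow 11.8 and 11.9 together for a non-fatal serious event that it judges unrelated to study product. The first requires a report to the sponsor; the second says that only attributed, unexpected Grade 3 or 4 events are reported.

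This would matter less if 11.9 were plainly an exemption from expedited reporting with a routine record behind it. In a transplant population, where serious events are frequent and usually explained by the transplant, such an exemption is reasonable. But the routine form is defined by reference to what is CTEP-AERS reportable, so narrowing the expedited rule also narrows the routine record.

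The trial gives live bacteria, under blinding, to children whose gut has been injured by conditioning. In a placebo-controlled trial an unforeseen harm shows as an imbalance between arms. A site that does not know the arm can easily put each single event down to the transplant. If attribution decides what is recorded, the DSMC may lack the by-arm frequency that Section 12.2 expects it to consider.

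**Working it through.** The plan states no figure on this point. The check sets the sections side by side.

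**1. The period in which attribution is not required under 11.8.** Dosing runs through Day 56 (Section 4.2.1) and follow-up through Day 120 (Section 4.1). For a patient who completes dosing the window ends at 56 + 30 = Day 86. The remaining 120 − 86 = 34 days (Days 87–120; 34/120 = 28% of post-graft follow-up) need attribution under 11.8 itself. If dosing stops early, the window ends earlier. The conflict therefore covers dosing plus 30 days.

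**2. Whether 11.5 resolves it.** Two gaps remain. It lets protocol-specific rules override the NCI guidelines, but does not mention the duty to report to the sponsor, which stands in 11.8 under the FDA heading. It also rests exceptions on an event being listed as expected, whereas 11.9 exempts unexpected events too if they are judged unrelated.

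**3. Routes to the adverse event form within 30 days of the last dose.** Section 11.10 gives two: the event is CTEP-AERS reportable, or it is attributed and Grade 3 or higher.

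| Serious event | CTEP-AERS reportable if Table A governs | CTEP-AERS reportable if 11.9 governs | Attributed, Grade 3+ | Form required if 11.9 governs |
|---|---|---|---|---|
| Grade 3–4, unexpected, attributed | yes | yes | yes | yes |
| Grade 3–4, expected, attributed | yes | no | yes | yes |
| Grade 3–4, not attributed | yes | no | no | **no** |
| Grade 1–2 with hospitalization of 24 hours or more, any attribution | yes | no | no | **no** |
| LBP-bacteremia | yes | yes | – | yes |
| Death | yes | yes | – | yes |

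The main loss is the unattributed non-fatal event. A Grade 1–2 hospitalization is lost as well, even if attributed.

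**4. What is collected elsewhere without a study-product attribution filter.**

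- Bloodstream infection, C. difficile diarrhea, antimicrobial use and parenteral or enteral nutrition (Section 7.2).
- Overall GvHD grade and skin, GI and liver stage (Section 9.2).
- Graft failure, relapse and death, which Sections 8.1, 8.2, 9.2 and 9.3 need for off-therapy and off-study status, the primary endpoint rule or the competing-risk analysis.
- Hospital days (Section 9.3, Exploratory Aim 7). As defined, these run from the conditioning admission to discharge, so it is unclear whether a readmission counts, and they carry no cause.

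No section provides for perforation, non-GvHD GI bleeding, or respiratory or renal failure when judged unrelated. The only event named as the safety measure is *L. plantarum* bacteremia (Exploratory Aim 8).

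**5. Deaths.** Sections 11.3.3 and 11.7 ask for expedited notice of late deaths only if related; 11.9 wants every death reported. For completers the wording differs over Days 87–120.

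**The case against.** The strongest defence is that 11.9 is a declared exception. Its heading says so, the note under Table A points to exceptions that follow, and both that note and the heading of 11.5 concern expedited reporting. On that reading the duty to report to the sponsor survives. This is a fair reading and probably the intended one. But 11.9 itself says reported, with no mention of expedited, and 11.10 then carries the narrowing into the routine form. The defence shows that the repair is easy, not that the text is clear.

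A reader might also infer four stronger points that the documents do not support:

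- *That unattributed serious events are recorded nowhere.* Several important event types are collected separately, as shown above. Appendix III also makes grossly bloody stool, and severe abdominal pain with or without ileus, Stage 4 gut criteria, so these are captured when judged to be GvHD. The case report forms are posted elsewhere (Section 12.0) and are not in the documents. What can be said is that the protocol text does not require the record.
- *That 11.2 and 11.8 demand every serious event whatever its attribution throughout.* They do not after 30 days from the last dose. Table A also marks Grade 1–2 events without hospitalization of at least 24 hours as not required.
- *That late unrelated deaths are lost.* Death is an off-study criterion, counts as an endpoint event if it comes before the outcome is determined, and is a competing event. It must be known through Day 120. Only the notification wording differs.
- *That the loss of power to detect a harm can be stated.* The documents give neither background rates of serious events nor the share that sites would attribute. They plan no powered comparison of such events, so any figure would rest on assumption alone.

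**Conclusion.** The inconsistency is real and should be fixed. Section 11.9 is narrower than 11.8 from the start of dosing to 30 days after the last dose, and 11.5 does not clearly decide between them. Read with 11.10, non-fatal serious events judged unrelated, and outside the separately collected types, need not be recorded as adverse events and so could not be compared by arm.

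The extent is bounded. The most specific risk of the product, LBP-bacteremia, is always reported and is compared by arm. The primary endpoint, the error rates and the analysis set are not affected. The number of events at stake cannot be estimated from the documents. The conclusion assumes that a site takes 11.9 at its word and that no case report form outside the documents collects these events. If such a form exists, the contradiction in wording remains but the data gap closes.

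**What to change.** 1. Reconcile 11.5, 11.8, 11.9 and 11.10. State that 11.9 exempts events from expedited CTEP-AERS reporting only, and say how sites meet the duty in 11.8 to report to the sponsor.
2. In 11.10, have every non-fatal serious adverse event through 30 days after the last dose entered on the routine adverse event form regardless of attribution.
3. Bring the death-notification wording in 11.3.3 and 11.7 into line with 11.9, so that one rule applies through Day 120.
4. Have the DSMC report tabulate deaths, bloodstream infections, C. difficile diarrhea and recorded serious events by arm, regardless of attribution.

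The cost is amendment wording and some extra routine data entry at sites, with no added expedited reports. The by-arm table of deaths, bloodstream infections and C. difficile needs no new data. Events not recorded as they occur are hard to recover later, so the change is worth making early.
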